4.3 Four monthly postal contact

Each fresh supply of materials will contain a brief form for completion by the participant (Appendix 8). This has the following purposes:

- i) confirmation that the materials arrived safely
- ii) collection of information about the preceding four months: any new fracture; any admission to hospital; and any change in residence
- iii) details of tablet compliance from the preceding week: whether the tablets have been taken, how often, and reason for stopping if applicable.

As a further measure of compliance, a five percent randomly selected subsample of recruits will be asked to return all unused supplies for a tablet count. A detailed protocol is provided in Appendix 9.

4.4 Additional information sought by post at four, twelve, twenty-four, thirtysix and forty-eight months after entry

Longer forms will be sent at four, twelve, twenty-four, thirty-six and forty-eight months (Appendix 10) which, in addition to the above, will collect the following information:

- i) falls in last week
- ii) the EQ-5 questionnaire
- iii) the SF-12 questionnaire
- iv) Diabetic or not, use of oral hypoglycaemics and/or insulin

4.5 Notifications by general practitioners

Stickers and the information sheet will ask the general practitioner to notify the Trial Office by phone if the participant:

- (i) sustains a new fracture
- (ii) moves to another practice

- (iii) has a suspected adverse event related to the trial, specifically developing renal insufficiency (creatinine greater than 250 micromols per l), renal stones, or hypercalcaemia (based on local reference standards)
- (iv) develops diabetes mellitus requiring oral hypoglycaemics and/or insulin.
- (v) dies (and cause of death)

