6.2 Measures of outcome

The principal clinical outcome measure is:

• all new low-energy fractures (other than face or skull) or clinical, radiologicallysupported, vertebral fractures reported.

Any apparent differences in fracture rates will be explored by subdivision into: proximal femoral, other lower limb/pelvis, distal forearm, other arm, clinical vertebral, and other fractures.

Other secondary outcome measures are:

- New radiologically-confirmed fractures
- Death after trial entry; the possible link between death and fracture will be examined in analyses of deaths occurring within three months of a new fracture
- General health status as measured by SF-12 and EQ-5D
- Hospital admissions after trial entry (number, length, place, and association with fracture)
- Change of residence category
- Falls (within five one-week window periods)
- Possible adverse effects (e.g. renal stones, gastrointestinal symptoms)
- New cancer registrations (Total, colon, breast, other)
- Deaths attributed to cardiovascular or cerebrovascular disease
- New cases of diabetes, taking oral hypoglycaemics and/or insulin

The ways in which these data will be displayed in the final report are illustrated in Appendix 11.

It is anticipated that other variables, such as bone density, genetic polymorphisms, and balance will be measured in explanatory studies and these will be described in separate protocols.

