8. ORGANISATION

8.1 Local organisation

- Each collaborating centre will identify a *clinical co-ordinator*. The responsibilities of this person will be to:
 - 1. establish the trial locally (for example, by getting agreement from clinical colleagues, facilitating local research ethics committee approval; identifying and appointing a local study nurse; and ensuring that all clinical staff involved in the care of people with fractures are informed about the trial)
 - 2. take responsibility for clinical aspects of the trial locally (for example, if any particular concerns emerge)
 - 3. notify the Trial Office of any unexpected clinical events which might be related to trial participation
 - 4. provide support and supervision for the local study nurse
 - 5. represent the centre at collaborators meetings

- Each clinical centre will appoint a *study nurse* to co-ordinate the day to day aspects of the trial. The responsibilities of this person will be to:
 - 1. keep local staff informed of progress in the trial
 - 2. keep regular contact with the local clinical co-ordinator, with notification of any problem or unexpected development
 - 3. to maintain regular contact with the Trial Office
 - 4. identify potential participants and keep a log of whether or not they are recruited (with reasons for non-participation)
 - 5. check eligibility, give information about the trial, and seek consent
 - 6. collect baseline data describing participants, and send these to the Trial Office
 - 7. supply initial materials to patients, if applicable
 - 8. telephone each person recruited two weeks after trial entry to check all is well and subsequently when judged necessary
 - 9. clarify the situation when the Trial Office fails to make a contact with a local participant, getting in touch by phone or a visit, if necessary
 - 10. seek further clinical details when a major trial event (such as a fracture or death) is reported to the Trial Office, even if this occurs in another hospital
 - 11. assist in the conduct of explanatory studies, if applicable
 - 12. provide support for participants in other ways if there are difficulties
 - 13. represent the centre at trial nurse meetings and collaborators meetings

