The incidence of adverse effects from the proposed dosage of vitamin D and calcium is anticipated to be very low - in the systematic review renal insufficiency or stones were reported for 4/4025 (0.1%) and gastro-intestinal disturbances for 93/3892 (2.4%).

Collaborators and participants may write to the chairman of the steering committee about any worries they may have about the trial. If concerns arise about particular side-effects or about particular types of participants, these will be relayed to the Chairman of the Data Monitoring Committee.

If clinically indicated, rapid unblinding of trial materials will be available through the trial office.

The Multicentre Research Ethics Committee for Scotland has approved the trial. The trial will be conducted according to the MRC Good Clinical Practice Guidelines (1998)²².

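### Section 4.5(iii) can be read as asking GPs to report renal insufficiency, renal stones and hypercalcaemia only when they suspect the trial, so GP-managed cases may be under-counted

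*Protocol*

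**What the plan says.** Protocol section 4.5 lists five things that a GP should telephone to the Trial Office. Item (i) is that the participant "sustains a new fracture", and item (iv) that the participant "develops diabetes mellitus requiring oral hypoglycaemics and/or insulin". Moving practice and death are equally plain. Item (iii) is worded differently: the GP notifies if the participant "has a suspected adverse event related to the trial, specifically developing renal insufficiency" (creatinine above 250 micromol/l), renal stones or hypercalcaemia, the last judged by local reference standards.

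Section 4.1 introduces the same list in the letter to the practice. It calls the items prespecified events and asks for notification if any of them occurs.

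Section 6.2 includes "Possible adverse effects (e.g. renal stones, gastrointestinal symptoms" among the secondary outcomes. Section 8.3 says that possible adverse effects will at first be the data monitoring committee's main concern, and quotes 4/4025 (0.1%) for renal insufficiency or stones from the systematic review.

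**The concern.** The three events in item (iii) need little or no attribution to be recognised. Renal insufficiency has a numerical creatinine threshold, hypercalcaemia has a laboratory reference range, and a stone is a diagnosis. In a randomised placebo-controlled comparison the control group answers the causal question, so a judgement at the point of notification can only discard events.

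On the literal reading, a GP who puts a rise in creatinine in an 80-year-old down to heart failure would have no reason to telephone. Possible hazards are part of the stated case for the trial (section 1.3). At about one event per thousand people, each lost report counts, and a low count could be taken for reassurance. Events that are never notified cannot be recovered at the analysis, so a statistical analysis plan could not repair this.

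**Working it through.** **1. Triggers side by side.** In section 4.5, four of the five items (fracture, change of practice, diabetes, death) have the event itself as the trigger. Only item (iii) adds suspected relation to the trial. Section 4.1 points the other way, towards notification on occurrence.

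**2. Other routes described in the protocol.**

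| Route | Asks for the three events by name? | What it could still catch |
|---|---|---|
| Four-monthly form (4.3) | No | Hospital admissions; reason for stopping tablets |
| Longer forms (4.4) | No | The same; they add diabetes but no renal or calcium item |
| Best contact (4.6) | No | Admission; serious illness |
| Hospital discharge summaries and letters (2.6) | No | Events with hospital contact |
| Nurse clarification and searches (4.7) | No | Queries on non-fracture admissions; searches cover fractures and deaths |
| National flagging (4.8) | No | Death and cancer only |

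Hospital-treated stones or renal failure therefore have partial routes with no relatedness condition. Stones, creatinine rises and hypercalcaemia managed in general practice have no named route other than item (iii).

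**3. The protocol's own figure.** 4/4025 = 0.099%, so the stated 0.1% reproduces (exact 95% confidence interval 0.03% to 0.25%). It does not cover hypercalcaemia.

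**4. Expected counts.** Inputs: planned recruitment of 6,500 (section 7.1), rate 4/4025 (section 8.3), and capture c, the share of events that reach the Trial Office by any route. The protocol gives no value for c, so a range is assumed.

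Expected recorded events = 6,500 × (4/4025) × c = 6.46 × c.

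**5. Power on one factorial margin.** Assumptions: equal allocation, so 3,250 per side; no losses; a rate of 0.1% on the unsupplemented side and 0.1% × RR on the supplemented side, where RR is the risk ratio; both multiplied by c. Power is the sum, over all pairs of binomial counts, of their joint probability whenever the two-sided Fisher exact test gives P < 0.05.

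| Capture c (assumed) | Expected events in 6,500 at 4/4025 | Power, RR 2 | Power, RR 3 | Power, RR 5 |
|---|---|---|---|---|
| 100% | 6.46 | 10% | 34% | 83% |
| 75% | 4.84 | 7% | 23% | 68% |
| 50% | 3.23 | 3% | 12% | 44% |
| 25% | 1.61 | <1% | 2% | 12% |

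For a fivefold risk the expected counts are 3.25 against 16.25 at full capture, and 1.62 against 8.12 at half capture. (Starting from the rounded 0.1%, the 75% row of the event column would be 6.5 × 0.75 = 4.9.)

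**The case against.** The strongest reply is that item (iii) is not a filter. Section 4.1 treats the list as prespecified events to be notified when they occur. The words after the condition name three events and define two of them objectively. On that reading the protocol has already designated these events as the suspected adverse effects, and the GP reports each one that develops. The letter and forms that GPs and participants receive are in appendices that are not shown, and they may be clearer. This stands as far as it goes: the conditional reading is the literal one, but not the only one.

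A reader might go further than the protocol allows in four ways.

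- *That the whole harm comparison depends on what GPs attribute.* It does not: admissions, hospital letters, reasons for stopping and best-contact reports carry no relatedness condition.
- *That the duty of the clinical co-ordinator in section 8.1 repeats the filter.* That duty is to "notify the Trial Office of any unexpected clinical events which might be related to trial participation". It is a general safety net, does not name these events, and is nowhere presented as the means of collecting this outcome. It removes nothing from section 4.5.
- *That the treatment comparison is biased towards safety.* Tablets are placebo-controlled and masked, so any filter should act similarly in all groups. No direction of bias follows.
- *That a stated share of events is lost, or that 0.1% is the expected rate for all three events.* The capture fractions are assumptions, and 4/4025 leaves out hypercalcaemia. It is also itself a reported rate, with ascertainment not described, so discounting it again may count under-reporting twice.

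Power is also poor with full reporting: about 10% for a doubled risk and 34% for a tripled one. Rewording will not make this a well-powered comparison.

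**Conclusion.** The point holds as an ambiguity with a plausible cost. Item (iii) literally ties notification to suspicion, section 4.1 implies that it should not, and no other described route asks for these events by name. Under-counting is possible, mainly for events managed by the GP, but it is not established.

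The size depends on the unknown capture fraction. About 6.5 renal events are expected in 6,500 people at full capture, and about 4.8, 3.2 or 1.6 at an assumed 75%, 50% or 25%. The clearest loss is for a large hazard: a fivefold risk would be detected with about 83% power at full capture, but with less than even chance (44%) at half. These figures rest on full recruitment, equal allocation, no losses, and the review's rate applying to the unsupplemented side over the trial's follow-up; the protocol does not state the last of these. What may be lost is accuracy of absolute rates and precision, for one example within a secondary outcome.

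**What to change.** Reword section 4.5(iii), and the GP sticker and letter to match, so that the GP notifies every new renal stone, every creatinine above the threshold already stated, and every case of hypercalcaemia, *whether or not thought related to the trial*. Record any view on causality as a separate field. This also brings section 4.5 into line with section 4.1. No change to section 8.1 is needed.

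The cost is a change of wording in the protocol and the GP materials, and a few more telephone reports, most of them unrelated to the tablets.

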4.6 Notifications by 'best contact'

The aim of the brief form and freepost envelope sent to 'best contacts' at the time of enrolment is to facilitate notification if the participant:

- (i) sustains a new fracture
- (ii) changes residence
- (iii) is admitted to hospital
- (iv) develops a serious illness/dies
- (v) has any difficulties with tablet delivery

4.7 Roles of study nurses after recruitment

• if a fracture, or death is reported

The Trial Office will seek details from the study nurses if any major trial event – new fracture or death – is reported. In most instances, details will be collected from local hospital records, but occasionally this may require contact with other hospital records departments or the general practice.

• if the Trial Office is uncertain about other trial outcomes

Occasionally the nurse will be contacted by the Trial Office to clarify other outcomes supplied by the patient, best contact or GP, such as, non fracture related admissions.

• *if the Trial Office fails to make a contact*

The Trial Office will liaise with the local study nurse if there is ever failure of contact with a participant, such that the materials are not delivered successfully, or a four-monthly form is not returned. In these circumstances the nurse will be supplied with full contact details for the participant, the 'best contact', and the general practitioner, and asked to clarify the situation. Any information being sought from a participant at this time may be most easily collected by telephone, but this will be left to the discretion of the local nurse.

• periodically during follow-up

The local study nurse will search local information systems for reports of new fractures or deaths amongst local trial recruits.

4.8 Flagging at Office for National Statistics

All participants will be flagged at the Office for National Statistics for notification of:

- (i) death
- (ii) cancer registration

5. DATA COLLECTION AND PROCESSING

Follow-up will continue for a median period of three years (range two to four years). Although further follow-up is anticipated, this is not part of this protocol.

Data from the various sources outlined above will be sent to the Trial Office in Aberdeen for processing. Staff in Aberdeen will work closely with study nurses to secure as complete and accurate data as possible. A random 10% sample of data will be double-entered to check accuracy. Extensive range and consistency checks will further enhance the quality of the data.

6. ANALYSIS PLANS

6.1 Ground rules for the statistical analyses

The statistical analyses will be based on all people randomised, irrespective of subsequent compliance with pill taking. The principal comparisons will be:

- (i) all those randomised vitamin D versus all those not allocated vitamin D
- (ii) all those randomised calcium versus all those not allocated calcium
- (iii) all randomised vitamin D and calcium versus all randomised Vitamin D alone versus all randomised calcium alone versus all randomised placebo

Evidence will be sought for an interaction between vitamin D and calcium.

The analyses will be based on two denominators:

- (i) all participants with data irrespective of length of follow-up, using 'time to an event' and multidecrement life-table analysis techniques
- (ii) all those with follow-up to 24 months

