7. SAMPLE SIZE AND FEASIBILITY

7.1 Sample size sought

The aim is to recruit about 6,500 people to the trial. This is based on a wish to identify a reduction of one fewer person per hundred allocated an active treatment sustaining a fracture each year over a median period of three years, if this was the true effect. Based on data from published trials in similar contexts the anticipated all fracture rate in the control groups is 15%. A total of 4000 participants would be needed in the analysis to have 80% power (2P<0.05) to detect an overall reduction to 12%. If the true effect is somewhat larger, say a 4% absolute benefit, the power will be over 90%. A trial of this size also has over 80% power to identify a 2% absolute difference in hip fracture rates (from 6% to 4%, or 5% to 3%).

The numbers sought have been inflated to 6,500 to take account of losses to followup. The main reason for 'loss to follow up' will be death. In the large Dutch trial¹² the rate was about 20% over three years, but we expect it to be higher overall (about 30%) because some of our participants will have sustained a recent proximal femoral fracture. Losses for other reasons, principally moving to other areas, are estimated from observations in one participating centre to be about 5%. The sample size has therefore been inflated by 35%.

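### The second denominator in section 6.1 keeps only those who survived and stayed to 24 months, and the protocol does not say that it ranks below the all-randomised analysis

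*Protocol*

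**What the plan says.** Protocol section 6.1 opens with a general rule: "The statistical analyses will be based on all people randomised, irrespective of subsequent compliance with pill taking". It lists the principal comparisons, the first being "all those randomised vitamin D versus all those not allocated vitamin D", and then states: "The analyses will be based on two denominators". These are:

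- Denominator (i) is "all participants with data irrespective of length of follow-up, using 'time to an event' and multidecrement life-table analysis techniques". It therefore keeps people whose follow-up is incomplete.
- Denominator (ii), by contrast, is restricted to "all those with follow-up to 24 months".

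The section does not say which of the two leads, whether a person who died before 24 months belongs to (ii), or whether fractures after 24 months count in (ii). Section 6.3 anticipates one principal analysis, two years after the last recruit, but does not say which denominator it uses.

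Two other places bear on the meaning of (ii). Section 5 gives follow-up as a median of three years, range two to four. Section 7.1 says: "The main reason for 'loss to follow up' will be death".

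**The concern.** Everyone is due at least two years of follow-up, so the calendar end of the trial removes nobody from (ii). The only ways out are death and loss. Membership is thus decided after randomisation, by something that may be related to the outcome. A participant who fractures at month 6 and dies at month 10 is not in (ii), and neither is the fracture. Section 6.2 expects such sequences, since it plans to examine deaths within three months of a new fracture.

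A survivors-only comparison is not protected by randomisation. Mortality is an outcome in section 6.2 and a possible ground for stopping in section 8.3, so equal removal from the groups cannot be taken for granted. Because the two denominators are unranked, the trial could report two differing fracture results with no prior rule on which one counts.

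**Working it through.** **The plan's own figure.** Section 7.1 states: "A total of 4000 participants would be needed in the analysis to have 80% power (2P<0.05) to detect an overall reduction to 12" per cent, from 15%. For two proportions with pooled variance under the null, n per group = [1.96 √(2p̄(1−p̄)) + 0.842 √(p₁(1−p₁) + p₂(1−p₂))]² / (p₁−p₂)². With 0.15 and 0.12 this gives 2,036 per half, 4,072 in all. Power at 4,000 is 79.3%. The stated figure reproduces.

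**Inputs for (ii).** From section 7.1: deaths about 30%, other losses about 5%, fracture 15% v 12%, 6,500 recruited. Assumptions: constant hazards over three years and equal halves.

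- Death: δ = −ln(0.70)/3 = 0.1189 per year
- Other loss: −ln(0.95)/3 = 0.0171 per year
- Both together: μ = 0.1360 per year
- Fracture, control: λ = −ln(0.85)/3 = 0.0542 per year
- Fracture, active: λ = −ln(0.88)/3 = 0.0426 per year

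**People dropped.** Retained at 24 months: exp(−2 × 0.1360) = 0.762. Dropped: 23.8%, or 0.238 × 6,500 ≈ 1,550, leaving about 4,950. Using the protocol's 35% total instead gives 23.3% (even accrual) to 25.0% (constant hazard). If all losses fell before 24 months, the share would be 35%.

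**Fracture cases dropped.** First fractures before death or loss, to 24 months: λ/(λ+μ) × [1 − exp(−2(λ+μ))] = 9.01% control and 7.17% active. Let fracture multiply the death hazard by k for one year. The fraction who fracture and are still present at 24 months is ∫₀² λ exp(−λt) exp(−2μ) exp(−(k−1)δ·min(1, 2−t)) dt; the fraction present without fracture is exp(−2(λ+μ)). The documents give no value for k, so k = 2 to 4 is an assumption.

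| k | Fracture cases dropped | Rates in (ii) | Relative risk in (ii) |
|---|---|---|---|
| 1 | 13.2% | 10.3% v 8.2% | 0.796 |
| 2 | 20.6% | 9.5% v 7.5% | 0.794 |
| 3 | 27.3% | 8.7% v 6.9% | 0.793 |
| 4 | 33.3% | 8.1% v 6.4% | 0.792 |

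The absolute rates fall as k rises. The relative risk hardly moves.

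**If the supplement also affects death directly.** Multiply δ in the active group by 0.8 or 1.25 (assumption). With k = 1 the relative risk stays at 0.796. With k = 2 to 4 it becomes 0.81 to 0.83 (multiplier 0.8) or 0.78 to 0.75 (multiplier 1.25). Bias therefore needs both a direct effect on death and a link between fracture and death.

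**Power.** At 15% v 12%: 79.3% with 4,000; 81.4% with 6,500 × 0.65 = 4,225; 87.1% with about 4,950.

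**The case against.** The general rule in 6.1 speaks of compliance with tablets, so it can be read as ruling out only selection by compliance. Denominator (i), listed first, already keeps partial follow-up through multidecrement life tables, and the person who fractures and then dies is counted there. A statistical analysis plan could rank the two and define deaths and the event window in (ii). Section 6.1 also covers measures taken at fixed times, such as SF-12 and EQ-5D at 24 months, for which a fixed-time denominator is ordinary. No bias in the relative risk follows from the protocol's own figures.

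Much of this stands. It removes any suggestion that these people are lost to the trial's analysis as a whole, and it lowers the severity. It does not remove the point. The protocol does not leave (ii) open for later: it fixes a fracture denominator that, on the plain reading, selects on survival, beside a rule of analysing everyone randomised. Reading (ii) as including deaths with known status is possible, but section 7.1 points the other way.

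A reader might also infer that (ii) takes power below the stated 80%. The documents do not support that. The 4,000 is the number left after losses, so the stated power already allows for them. Power falls to about 72% (10.3% v 8.2% in about 4,950) only if fractures are also counted only to 24 months, which the protocol does not say. On that window even a time-to-event analysis of all 6,500 has about 526 events and 79% power, so much of the shortfall would come from the shorter window.

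**Conclusion.** The point holds in limited form. On the plain reading, (ii) conditions on survival and retention to 24 months, conflicts with the all-randomised principle, and has no stated rank. It drops about 24% of participants (23% to 25% under the accrual patterns tried). It drops about 13% of fracture cases to 24 months if fracture does not raise mortality, and 21% to 33% if it does so two- to fourfold for a year.

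If fracture raises mortality, the absolute rates in (ii) are understated: the control rate is 9.5% to 8.1%, against the 10.3% implied by the fracture hazard alone. The relative risk stays near 0.79 unless the supplements affect death other than through fracture, which the trial itself examines. These sizes rest on constant hazards, equal halves and the assumed values of k.

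This should be corrected, but it does not threaten the trial: denominator (i) is sound and the sample size is unaffected.

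**What to change.** In section 6.1:

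- Name denominator (i) as the principal fracture analysis: time to first fracture in all randomised, with death as a competing decrement.
- For fracture, replace (ii) with the 24-month cumulative incidence in all randomised, read from the same multidecrement life table. On the assumptions above this would be about 9.0% v 7.2%.
- If a 24-month completers table is kept, label it descriptive and state how deaths and fractures after 24 months are handled in it.
- Fixed-time measures such as SF-12 and EQ-5D may keep a 24-month respondent denominator.

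The cost is a change of wording. No new data are needed: deaths are already notified through national flagging (section 4.8), and study nurses already search local systems for fractures and deaths (section 4.7).
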